7.4 Derived Data

The following variables will be derived from the collected data:

- ❖ **Age:** The age will be calculated as the exact number of days between the date of birth and date of entry into study converted to years (i.e. difference in days/365.25).
- ❖ **Body Mass Index (BMI):** BMI is obtained by dividing the weight (kg) at enrollment by the square of height (m) i.e. weight (kg)/ height² (m).

CONFIDENTIAL AND PROPRIETARY

This document contains information that is confidential and proprietary to Smith & Nephew PLC and Smith & Nephew, Inc. and is intended for use only by Smith+Nephew and its manufacturer. It shall not be reproduced or copied in whole or in part, nor shall the contents be disclosed by any means without prior written permission from Smith+Nephew, nor shall anyone make any use of it that is contrary to the expressed or implied wishes of Smith+Nephew.

Statistical Analysis Plan

Multicenter Clinical Observation Using the Cementless Version of the
POLARSTEM™

Number: D10070
ST: 1133
Version: 1.0, 30-Nov-2021
Page: 10 of 19

- ❖ **Baseline:** Preoperative examination visit is considered as the baseline visit for all parameters for which data is collected at that time point.
- ❖ **Safety population indicator variable:** A binary variable will be defined if the patient receives study treatment then the patient is included in the safety population or not. Only patients indicated as included in the safety population will be used in the safety population analysis.
- ❖ **FAS set indicator variable:** A categorical variable will be defined to indicate if the patient receives study treatment and attends at least one post-baseline assessment then the patient is included in the full analysis set. Only the patients in the included category will be included in the full analysis set.
- ❖ **Per-protocol set indicator variable:** A categorical variable will be defined to indicate if the patient is in the full analysis set and have no significant protocol deviations and meet the inclusion/exclusion criteria. Only the patients in the included category will be included in the per-protocol analysis set.
- ❖ **Visit Interval:** days between baseline assessment and Study Visit defined as: Date of Study Visit – date of baseline assessment.
- ❖ **Survival time (days):** End of study/Death/Loss to Follow-up/revision date – baseline assessment date+1; In months, divide days by 30.4375; In years, divide days by 365.25.
- ❖ **Revision:** Binary indicator variable for presence of revision
- ❖ **Adverse event:** Binary indicator for whether a patient experiences at least one adverse event.
- ❖ **Scores (HHS and WOMAC from HOOS):** The global scores or scores under each dimension of the questionnaire under consideration will be determined per specific scoring instructions for each questionnaire.
 - ❖ Harris Hip Score (HHS)
 - ❖ Algorithms used for scoring each of the 10 items (components) of the HHS as well as the domains (pain, function, AoD and ROM) of the HHS and total HHS are presented below:
 - ❖

CONFIDENTIAL AND PROPRIETARY

This document contains information that is confidential and proprietary to Smith & Nephew PLC and Smith & Nephew, Inc. and is intended for use only by Smith+Nephew and its manufacturer. It shall not be reproduced or copied in whole or in part, nor shall the contents be disclosed by any means without prior written permission from Smith+Nephew, nor shall anyone make any use of it that is contrary to the expressed or implied wishes of Smith+Nephew.

Statistical Analysis Plan

Multicenter Clinical Observation Using the Cementless Version of the
POLARSTEM™

Number: D10070
ST: 1133
Version: 1.0, 30-Nov-2021
Page: 11 of 19

Harris Hip Score (HHS) scores per item and domain			
Item	Original Response	Likely scores per Item	Domains (Range of Scores)
Pain	None or ignores it	44	Pain Domain (0 to 44)
	Slight, minimal, no compromise in activities	40	
	Mild pain, no effect on average activities, rarely moderate pain with unusual activity; may take aspirin	30	
	Moderate pain; tolerable but makes concessions to pain. Some limitation of ordinary activity or work. May require occasional pain medication stronger than aspirin	20	
	Marked pain, serious limitation of activities	10	
	Totally disabled, crippled, pain in bed, bedridden	0	
Limp	None	11	Function Domain (0 to 47) {Sum of all items within subdomain}
	Slight	8	
	Moderate	5	
	Severe	0	
Support	None	11	
	Single cane for long walks	7	
	Single cane most of the time	5	
	One crutch	3	
	Two canes	2	
	Two crutches or not able to walk	0	
Distance walked	Unlimited	11	
	Six blocks	8	
	Two or three blocks	5	
	Indoors only	2	
	Bed and chair only	0	
Sitting	Comfortably in ordinary chair	5	
	On a high chair for 30 minutes	3	
	Unable to sit comfortably in any chair	0	

CONFIDENTIAL AND PROPRIETARY

This document contains information that is confidential and proprietary to Smith & Nephew PLC and Smith & Nephew, Inc. and is intended for use only by Smith+Nephew and its manufacturer. It shall not be reproduced or copied in whole or in part, nor shall the contents be disclosed by any means without prior written permission from Smith+Nephew, nor shall anyone make any use of it that is contrary to the expressed or implied wishes of Smith+Nephew.

Statistical Analysis Plan

Multicenter Clinical Observation Using the Cementless Version of the
POLARSTEM™

Number: D10070
ST: 1133
Version: 1.0, 30-Nov-2021
Page: 12 of 19

Public transportation	Yes, possible	1	
	No, unable	0	
Stairs	Normally without using a railing	4	
	Normally using a railing	2	
	In any manner	1	
	Unable to do stairs	0	
Socks/Shoes	With ease	4	
	With difficulty	2	
	Unable	0	
Range of Motion (ROM)	Flexion = FLEX+EXT-FLEX_ZERO	N/A	
	Movement = ABD+ADD-ABD_ZERO	N/A	
	Rotation = ER+IR-ER_ZERO	N/A	
ROM subscore	Flexion+Movement+Rotation		Range of Motion Domain (0 to 5)
	0 to 29	0	
	30 to 59	1	
	60 to 99	2	
	100 to 159	3	
	160 to 209	4	
	≥ 209	5	
Leg Length Difference (in mm)	None	N/A	
	Ipsilateral longer (LL_DIF_LONG)	N/A	
	Ipsilateral shorter (LL_DIF_SHORT)	N/A	
Absence of Deformity (AOD)	IF (FLEX_ZERO = . OR FLEX_ZERO < 31) AND (ABD_ZERO = . OR ABD_ZERO < 11) AND (ER_ZERO = . OR ER_ZERO < 11) AND LL_DIF_LONG < 33 AND LL_DIF_SHORT < 33 THEN AODScore = 4	0 or 4	Absence of Deformity Domain (0 to 4)
Total HHS		Sum of all domain scores per subject	Sum of all domain scores per subject

CONFIDENTIAL AND PROPRIETARY

This document contains information that is confidential and proprietary to Smith & Nephew PLC and Smith & Nephew, Inc. and is intended for use only by Smith+Nephew and its manufacturer. It shall not be reproduced or copied in whole or in part, nor shall the contents be disclosed by any means without prior written permission from Smith+Nephew, nor shall anyone make any use of it that is contrary to the expressed or implied wishes of Smith+Nephew.

Statistical Analysis Plan

Multicenter Clinical Observation Using the Cementless Version of the
POLARSTEM™

Number: D10070
ST: 1133
Version: 1.0, 30-Nov-2021
Page: 13 of 19

Note: The maximum possible score for the HHS is 100.			

For the WOMAC from HOOS, algorithms used in deriving the pertinent endpoints are as presented below.

WOMAC from HOOS Stiffness, Pain, and Physical Function Raw Scores			
Items/Questions within each domain		Range of Individual RAW Scores for each item	Possible Range of Scores by Domain
S1	Stiffness Stiffness in the morning . Stiffness later in the day	None = 0; Slight = 1; Moderate = 2; Severe = 3; Extreme = 4	0 to 8
S2			
P1	Pain Walking on flat	None = 0; Slight = 1; Moderate = 2; Severe = 3; Extreme = 4	0 to 20
P2	Stair climbing		
P3	At night while in bed		
P4	Sitting or lying		
P5	Standing upright		
A1	Physical Function Descending stairs	None = 0; Slight = 1; Moderate = 2; Severe = 3; Extreme = 4	0 to 68
A2	Ascending stairs		
A3	Rising from sitting		
A4	Standing		
A5	Bending on floor		
A6	Walking on flat		
A7	Getting in/out of car		
A8	Going shopping		
A9	Putting on socks		
A10	Rising from bed		
A11	Taking off socks		
A12	Lying in bed		
A13	Getting in/out bath		
A14	Sitting		
A15	Getting on/off toilet		
A16	Heavy domestic		
A17	Light domestic		
Total RAW WOMAC Score		Sum of Stiffness, Pain, and Physical Function scores	0 to 96

CONFIDENTIAL AND PROPRIETARY

This document contains information that is confidential and proprietary to Smith & Nephew PLC and Smith & Nephew, Inc. and is intended for use only by Smith+Nephew and its manufacturer. It shall not be reproduced or copied in whole or in part, nor shall the contents be disclosed by any means without prior written permission from Smith+Nephew, nor shall anyone make any use of it that is contrary to the expressed or implied wishes of Smith+Nephew.

Statistical Analysis Plan

Multicenter Clinical Observation Using the Cementless Version of the POLARSTEM™

Number: D10070
ST: 1133
Version: 1.0, 30-Nov-2021
Page: 14 of 19

Algorithms for Calculating Transformed WOMAC from HOOS scores

WOMAC Subdomain	Original score = sum of the following items from Table 2	Possible Raw score range
Pain	P1 to P5	20
Stiffness	S1 to S2	8
Function	A1 to A17	68
Total	Sum{(P1 to P5), (S1 to S2), (A1 to A17)}	96
Transformed Score (per subdomain) = $100 - \{(actual\ raw\ score/possible\ raw\ score\ range)\times 100\}$		

Each WOMAC subdomain score is transformed independently to a value that would range between 0 and 100. For each transformed score, a value of 100 is indicative that the subject has no problems while a score of 0 is indicative of severe problems within each subdomain.

- ❖ **Enrolled Subject:** A subject is considered to be enrolled into the trial when they sign informed consent forms.
- ❖ **Withdrawn Subject:** A withdrawn subject will be considered as one who does not complete the study because of to loss to follow-up or the early termination or any other known reason.
- ❖ **Completed Subject:** This study has been terminated early, a subject will be considered as having completed the study if he/she completed the 10 year visit for the study prior to its termination.

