2.1 Patient selection

Patients enrolled in this multicenter clinical observation will have at least one of the indications listed below and meet all of the inclusion criteria. Patients meeting any of the exclusion criteria are not eligible for this study.

Indications

- Primary or secondary coxarthrosis
- Rheumatoid arthritis
- Developmental dysplasia of the hip (Crowe type I and II)
- Fracture or avascular necrosis of the femoral head

Inclusion criteria

- Patient has no general medical contraindication to surgery
- Informed consent to participate in the MCO signed by the patient
- Routine radiographic assessment is possible
- Patient is likely to comply with study follow-up requirements
- Primary total hip replacement (THR) to the affected side, unilateral or bilateral

Exclusion criteria

- Previously failed endoprosthesis and /or THR components in relevant hip
- History of infection in the affected joint; systemic infections
- Grossly insufficient femoral or acetabular bone stock in the involved hip
- Charcot joint disease or other severe neurosensory deficit
- Severe spinal disorders
- Age of patient at date of surgery > 75 years

- High comorbidity
- Cemented acetabular cup

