5 STUDY ENDPOINTS

5.1 Primary Endpoint

Short term, medium term and long term survival rates at 3 months and at 1, 3, 5, and 10 years.

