7.5 Baseline Data

Baseline characteristics with information available either at the preoperative or at the operative visit would be summarized using descriptive characteristics for continuous¹ or categorical² data but not only limited to the following variables:

CONFIDENTIAL AND PROPRIETARY

This document contains information that is confidential and proprietary to Smith & Nephew PLC and Smith & Nephew, Inc. and is intended for use only by Smith+Nephew and its manufacturer. It shall not be reproduced or copied in whole or in part, nor shall the contents be disclosed by any means without prior written permission from Smith+Nephew, nor shall anyone make any use of it that is contrary to the expressed or implied wishes of Smith+Nephew.

Statistical Analysis Plan

Multicenter Clinical Observation Using the Cementless Version of the
POLARSTEM™

Number: D10070
ST: 1133
Version: 1.0, 30-Nov-2021
Page: 15 of 19

- Body Mass Index (BMI)¹
- Operative data² (i.e. surgery access)
- Charnley classification²
- Physical activity²
- Medication²
- Previous ipsilateral surgeries²
- Local risk factors²
- General risk factors²
- Type of anesthesia²
- Surgery time¹
- Cup type²
- Cup size²
- Cup cemented²
- Stem size²
- Stem cemented²
- Head type²
- Head size²
- Neck length²
- Articulation²
- Operated Hip² (Right, Left, Bilateral).
- Fixation with additional screws²
- Tribological pairing²
- Primary diagnosis at enrollment²
- Intraoperative complications²
- Medical History² (i.e. general risk factors, diabetes, heart/circulatory, etc.)
- Local early postoperative complications²
- General early postoperative complications²

CONFIDENTIAL AND PROPRIETARY

This document contains information that is confidential and proprietary to Smith & Nephew PLC and Smith & Nephew, Inc. and is intended for use only by Smith+Nephew and its manufacturer. It shall not be reproduced or copied in whole or in part, nor shall the contents be disclosed by any means without prior written permission from Smith+Nephew, nor shall anyone make any use of it that is contrary to the expressed or implied wishes of Smith+Nephew.

Statistical Analysis Plan

Multicenter Clinical Observation Using the Cementless Version of the POLARSTEM™

Number: D10070
ST: 1133
Version: 1.0, 30-Nov-2021
Page: 16 of 19

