7.10 Analysis of Primary Endpoint

- Short term, medium term and long term survival rates.
- Survival rates will be presented with a 95% confidence intervals at 3 months and at 1 year, 3 year, 5 year and 10 year postoperative time points from Kaplan-Meier product limit estimates.
- The revisions (by type of revision) will be tabulated and/or listed.

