7.15 Changes in Analysis Methods Specified in the Protocol

There is a discrepancy in the protocol in regards to the sample size requirements for this study. In the “Study Design” section of the protocol, it is stated that a minimum of 225 subjects will be enrolled in 3 sites whereas in the “Sample Size Consideration” of the protocol, it is stated that “Sample size estimations have been made on the assumption that for a valid statistical data analysis according to Kaplan-Meier, at least 100 implants surviving 10 years are necessary. Over a period of 10 years, a drop-out rate of 30% should be considered. Therefore, 150 initial implantations are needed in each group”.

A total of 225 subjects was eventually enrolled and implanted with the study device.

CONFIDENTIAL AND PROPRIETARY

This document contains information that is confidential and proprietary to Smith & Nephew PLC and Smith & Nephew, Inc. and is intended for use only by Smith+Nephew and its manufacturer. It shall not be reproduced or copied in whole or in part, nor shall the contents be disclosed by any means without prior written permission from Smith+Nephew, nor shall anyone make any use of it that is contrary to the expressed or implied wishes of Smith+Nephew.

Smith+Nephew

Statistical Analysis Plan

Multicenter Clinical Observation Using the Cementless Version of the
POLARSTEM™

Number: D10070
ST: 1133
Version: 1.0, 30-Nov-2021
Page: 19 of 19

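### SAP 7.4 starts implant survival time at the preoperative visit, up to 45 days before surgery, so the postoperative survival rates, chiefly the 3-month rate, can be overstated

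*SAP*

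**What the plan says.** SAP 5.1 makes implant survival the primary endpoint: "Short term, medium term and long term survival rates at 3 months and at 1, 3, 5, and 10 years". SAP 7.10 says that these rates will be presented "at 3 months and at 1 year, 3 year, 5 year and 10 year postoperative time points from Kaplan-Meier product limit estimates". Protocol 1.3 defines the event as stem revision for any reason.

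The time variable is defined in SAP 7.4 (Survival time): "End of study/Death/Loss to Follow-up/revision date – baseline assessment date+1". The same section defines baseline: "Preoperative examination visit is considered as the baseline visit for all parameters for which data is collected at that time point". Protocol 3.3, Table 1, sets the window for the preoperative visit at 45 to 0 days.

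Neither document names the date of surgery or implantation as the time origin. SAP 7.15, the section for departures from the protocol, discusses only the sample size.

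**The concern.** The clock starts before surgery, but the result is labelled as time since surgery. The full analysis set (SAP 7.2) contains only subjects who received the study treatment. The days between the preoperative visit and the operation are therefore event-free by construction.

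Those days lengthen each hip's recorded survival by an amount that depends on when the visit was booked. A revision shortly before a reporting mark can then be counted after it. The errors run in the device's favour, vary between patients, and weigh most on the shortest interval. Two of the five primary time points, 3 months and 1 year, are short enough for this to matter at all.

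**Working it through.** The documents state no survival or revision rate, so there is no figure of the plan's own to reproduce. The check is date arithmetic, followed by an illustration on stated assumptions.

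**Inputs from the documents.** The formula and unit conversions are in SAP 7.4 (30.4375 days per month, 365.25 per year). The gap L between preoperative visit and surgery is 0 to 45 days (Protocol Table 1). The number implanted is 225 (SAP 7.15).

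**Step 1: recorded time.** A revision on postoperative day k gets time k + L + 1 under SAP 7.4, against k + 1 with a surgery origin. For a gap common to all hips, S_SAP(t) = S_surgery(t − L), which is never below S_surgery(t).

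**Step 2: days covered.** The 3-month mark is 3 × 30.4375 = 91.3 days and the 1-year mark is 365.25 days. The last postoperative day counted is floor(mark − 1 − L):

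| Mark | L = 0 | L = 45 | 45 days as share of interval |
|---|---|---|---|
| 3 months | day 90 | day 45 | 45/91.3 = 49% |
| 1 year | day 364 | day 319 | 45/365.25 = 12% |
| 3 years | day 1094 | day 1049 | 45/1095.75 = 4.1% |
| 5 years | day 1825 | day 1780 | 45/1826.25 = 2.5% |
| 10 years | day 3651 | day 3606 | 45/3652.5 = 1.2% |

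For example, a revision on day 60 with L = 45 gets 60 + 45 + 1 = 106 days and falls after the 3-month mark. With a surgery origin it gets 61 days and counts.

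**Step 3: share of revisions displaced.** Two failure patterns are assumed: evenly spread, and front-loaded (exponential, mean 30 days for the 3-month calculation and 90 days for the 1-year one). Daily probabilities are summed over days 0-90 or 0-364.

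| Interval and pattern | L = 7 | L = 14 | L uniform 0-45 | L = 45 |
|---|---|---|---|---|
| 3 months, even | 7.7% | 15.4% | 24.7% | 49.5% |
| 3 months, front-loaded | 1.3% | 3.0% | 6.7% | 17.6% |
| 1 year, even | 1.9% | 3.8% | 6.2% | 12.3% |
| 1 year, front-loaded | 0.1% | 0.3% | 0.5% | 1.1% |

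**Step 4: overstatement.** This is the displaced share times the cumulative revision proportion at the mark. With an assumed 1% revised:

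- 3 months, for L = 7, 14, uniform and 45: 0.08, 0.15, 0.25 and 0.49 points if even; 0.01, 0.03, 0.07 and 0.18 points if front-loaded.
- 1 year, for L uniform and 45: 0.06 and 0.12 points if even; about 0.01 points or less if front-loaded.

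The result scales in proportion to the assumed revision rate. At 0.5% and 2% revised by 3 months, the uniform-gap figures are 0.03 and 0.13 points (front-loaded) or 0.12 and 0.49 points (even).

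**Step 5: Kaplan-Meier simulation.** The settings were 225 hips, uniform gaps of 0-45 days, 30% dropout over 10 years, constant hazard within each period, and 2000 runs per scenario. With assumed true revision of 0.5-2% at 3 months and 1-3% at 1 year, the mean rise was 0.13 to 0.48 points at 3 months and 0.04 to 0.09 points at 1 year. The SAP version was lower in under 1% of runs. This can happen because unequal gaps also change the risk sets slightly.

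**Step 6: comparison with sampling error.** With 1% revised, the 95% half-width is 1.96 × sqrt(0.01 × 0.99/225) = 1.3 points. One displaced hip is 1/225 = 0.44 points.

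**The case against.** **The text may be ambiguous.** The baseline definition is limited to parameters collected at the preoperative visit, and implant survival is not one of them. SAP 7.5 takes "Baseline characteristics with information available either at the preoperative or at the operative visit", and SAP 7.10 speaks of postoperative time points, so a programmer might use the surgery date anyway. But the limiting clause only says which parameters take their baseline value from that visit. SAP 7.5 governs descriptive summaries. Neither supplies another date for the survival formula, and using the surgery date would depart from the rule as written.

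**The effect is small.** This stands. With 225 hips, 1% revised and uniform gaps, the expected number of hips displaced at 3 months is 225 × 0.01 × 0.067 = 0.15 (front-loaded) to 225 × 0.01 × 0.247 = 0.56 (even). By a Poisson approximation, no hip moves in about 86% or 57% of such studies. At 1 year the expected numbers are 0.01 and 0.14, and no hip moves in about 99% or 87%. More often than not the early rates would not change materially. The largest figures also require every hip to be at the edge of the visit window.

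**No decision hangs on it.** The study is single-arm, SAP 7.10 sets no performance goal or test for survival, and the protocol's sample size rests on 10-year survival. That is correct and limits the consequences. However, SAP 5.1 makes the early rates primary results, and they will be read as such.

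**There may be no bias at all.** If every preoperative visit fell on the day of surgery, the two origins coincide. The actual gaps are not in the documents, so the rates can be overstated; it is not shown that they are.

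**Conclusion.** The concern holds. As written, the time origin in SAP 7.4 contradicts the postoperative time points in SAP 7.10, and following it shifts the early survival rates in the device's favour whenever the preoperative visit precedes surgery and a revision falls in the displaced days.

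The textual mismatch is certain; its numerical effect is modest and rests on assumed revision rates, failure timing and gaps. Only the 3-month rate is at risk of a visible shift. At 1 year the effect is slight, and at 10 years it is negligible. The bias stays below sampling error in the scenarios examined. It should be fixed because it is a systematic and easily avoided error in the definition of the primary endpoint.

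**What to change.** In SAP 7.4, define survival time as the revision or censoring date minus the index surgery date of the hip concerned, and state whether one day is added. Keep the preoperative visit as baseline for HHS and HOOS. Whether survival is analysed per hip or per subject is a separate question; the date of implantation is the right origin in either case.

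Visit Interval in SAP 7.4 uses the same baseline date and could be dated from surgery for consistency. The SAP states no use for that variable, so no effect on results is claimed.

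The cost is one or two lines of SAP text. The surgery date should already be on file, because the protocol's age exclusion is applied at that date (Protocol 2.1: "Age of patient at date of surgery > 75 years"). The CRF was not available to confirm this.

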1.3 Objectives

The goal of this multicenter clinical observation is to validate short-, mid-, and long-term outcome (efficacy and safety) of the POLARSTEM®.

Efficacy evaluations

- Evaluation of function, range of motion (ROM) and pain as assessed by Harris Hip Score, Hip disability and osteoarthritis outcome score (HOOS) [7, 8], an extension of the Western Ontario and McMaster Universities Osteoarthritis Index (WOMAC).
- Radiographic changes as defined by radiolucent lines, osteolysis, hypo- and hypertrophy, implant loosening or migration

Safety evaluations

- Intra- and perioperative device-related adverse events (AE) and complications up to discharge
- Postoperative AE up to 10 years

Long-term survivorship will be calculated according to Kaplan-Meier with stem revision due to any reason as endpoint.

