7.3 Handling of Missing, Incomplete and Repeat Data

Missing and incomplete data are usually due to lost to follow-up, revision, death and patient withdrawal. A complete accountability along with the explanation for lost-to-follow-up, death, revision, and withdrawn patients will be provided in the final study report and these subjects will be treated as censored at the date of lost-to-follow up in the survival analysis. The missing due to revision will be treated as device failure. A complete assessment of the informative/non-informative missing data will be performed. In case of missing outcome values at designated time points, the last observation carried forward (LOCF) method will be used.

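### The SAP's primary survival analysis never states the protocol's event, stem revision for any reason, and section 7.3 both censors revision and counts it as failure

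*SAP*

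**What the plan says.** Protocol 1.3 fixes both the component and the cause: "Long-term survivorship will be calculated according to Kaplan-Meier with stem revision due to any reason as endpoint".

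The SAP makes survival the primary endpoint in 5.1, "Short term, medium term and long term survival rates at 3 months and at 1, 3, 5, and 10 years", and section 7.10 estimates it by Kaplan-Meier with 95% confidence intervals. Neither section names an event. The same is true of the fallback in 7.1, a survival proportion to be used if the data do not allow Kaplan-Meier.

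The terms a programmer would work from are in 7.4. They are a revision variable, "Binary indicator variable for presence of revision", and a survival time that runs to "End of study/Death/Loss to Follow-up/revision date". Neither is limited to the stem.

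Section 7.3 gives the censoring rule: "lost-to-follow-up, death, revision, and withdrawn patients will be provided in the final study report and these subjects will be treated as censored". The next sentence reads "The missing due to revision will be treated as device failure".

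Section 7.10 adds "The revisions (by type of revision) will be tabulated and/or listed". Section 7.15, which is for changes from the protocol's analysis methods, deals only with sample size.

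**The concern.** The study exists to validate one stem, and the survival rate is its headline result. The event behind that rate should be readable from the SAP without interpretation. As the text stands, two programmers could define it differently and both point to the SAP.

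The readings err in opposite directions. If every revision is an event, a hip whose cup or head was revised while the stem stayed in place counts as a failure, and survival comes out lower than the protocol's definition would give. If the censoring sentence in 7.3 is followed, revisions are not events at all and survival is overstated. A third gap is the cause: the protocol counts stem revision for any reason, and the SAP's device-failure wording does not say that every reason counts.

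**Working it through.** The documents contain no survival target, revision rate or revision count, so there is no figure of the plan to reproduce. The check compares the texts and then sizes the effect under stated assumptions.

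**Texts side by side**

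| Element | Protocol 1.3 | SAP |
|---|---|---|
| Component | stem | not stated (5.1, 7.4, 7.10) |
| Reason | any | not stated |
| Role of revision | event | censored, then device failure (7.3) |
| End of survival time | not detailed | any revision date (7.4); no event or censoring flag given there |
| Declared change of event | – | none (7.15) |

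Stem-sparing revision is a real possibility. Protocol 4.1 pairs the stem with a separate cementless cup, SAP 7.5 summarises cup and head data, and SAP 7.10 expects more than one type of revision. That last phrase is undefined and applies to a table or listing, not to the Kaplan-Meier event.

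**Size if every revision is an event**

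Inputs:
- Stem revision at 10 years, s = 2% (assumed).
- Stem-sparing revision at 10 years, x = 0, 1, 2 or 4% (assumed).
- Drop-out of 30% over 10 years (protocol 2.2).
- n = 225 (SAP 7.15). This counts subjects; the number of implants is higher if there are bilateral cases.
- Constant, independent hazards (assumed).

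Formulas:
- Protocol event: S_stem = 1 − s = 0.980.
- Any revision: S_any = (1 − s)(1 − x). For x = 2%, 0.98 × 0.98 = 0.9604.
- Extra events without drop-out: 225 × (S_stem − S_any).
- Events with drop-out: E = 225 × h/(h + c) × (1 − exp(−10(h + c))), with h = −ln(S)/10 and c = −ln(0.7)/10 = 0.03567.
- Stem only: h = 0.00202, so E = 225 × 0.0536 × (1 − 0.98 × 0.7) = 3.79.
- Any revision, x = 2%: h = 0.00404, so E = 225 × 0.1018 × (1 − 0.9604 × 0.7) = 7.50.

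| x | S_any | Points below 98.0% | Extra events, no drop-out | Events, 30% drop-out | Extra events, 30% drop-out |
|---|---|---|---|---|---|
| 0% | 98.0% | 0 | 0 | 3.79 | 0 |
| 1% | 97.0% | 0.98 | 2.21 | 5.64 | 1.86 |
| 2% | 96.0% | 1.96 | 4.41 | 7.50 | 3.72 |
| 4% | 94.1% | 3.92 | 8.82 | 11.22 | 7.44 |

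Differences are taken before rounding. With s = 3% the gaps for x = 1, 2 and 4% are 0.97, 1.94 and 3.88 points, so the assumed stem rate hardly matters.

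**Size if revisions are censored**

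With no events every Kaplan-Meier factor is 1, so survival is 100% whatever the number of revisions. For comparison, take 225 hips with 30% drop-out and revisions spread evenly over 10 years (assumed counts). Four stem revisions as events give 97.9% (standard error 1.05 points). Four stem plus four stem-sparing revisions, all counted, give 95.8% (standard error 1.48 points).

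**The case against.** The strongest reply is that the protocol's event is still in force. The SAP presents itself as detailing the analysis of that protocol, and because 7.15 declares no change, the SAP may simply be abbreviating. The study device is the stem, so device failure in 7.3 can be read as stem failure. Nothing in 7.4 expressly ties the revision flag to the Kaplan-Meier event. The conflict in 7.3 looks like loose drafting: "these subjects will be treated as censored at the date of lost-to-follow up in the survival analysis" cannot fit a revised patient, and 7.4 lists the revision date separately from loss to follow-up.

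Much of this stands as a guide to intent. Revision is almost certainly meant to be an event, and the 100% result is an unlikely outcome. But no SAP section says that device means stem, that every reason counts, or what happens to a hip with a stem-sparing revision. The missing link in 7.4 adds to the uncertainty.

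On size, the rates are assumed. With a standard error of 1.05 points the 95% half-width is about 1.96 × 1.05 = 2.1 points, so the 1% and 2% scenarios stay within it and only 4% exceeds it. Counting every revision would also not flatter the device. Both points are fair, but the shift is a difference in what is estimated, not sampling noise.

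The TFL shells, which SAP section 2 names as a related document, may label the event; they were not available. SAP 7.4 says the study was terminated early, so later data on a hip after a stem-sparing revision may be missing. Such a hip is censored when its stem status was last known, so no new data are needed.

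**Conclusion.** The concern holds. The SAP does not carry over the protocol's survivorship event, and 7.3 contradicts itself on whether revision is censored. The textual finding is firm and needs no assumption.

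The numerical effect is conditional. With assumed 10-year stem revision of 2% and stem-sparing revision of 1% to 4%, counting every revision lowers 10-year survival by 1.0 to 3.9 points. At 2% for each, with 30% drop-out, it roughly doubles the events, from 3.8 to 7.5. The effect is zero if no revision spared the stem. This should be corrected before the final analysis is programmed, because it decides what the primary result means.

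**What to change.** - **SAP 5.1, 7.4 and 7.10:** state that the event is revision of the stem for any reason, as in protocol 1.3, timed at the date of that surgery. Apply the same definition to the fallback proportion in 7.1.
- **SAP 7.4 and 7.10:** state that a revision not involving the stem is not an event, that the hip stays at risk, and that without later data it is censored at its last known stem status. This agrees with protocol 3.4, which ends observation at explantation of the device.
- **SAP 7.3:** remove revision from the list of censored subjects and keep one sentence making stem revision the failure.
- **Interim analysis (SAP 6.3):** record which event the 5-year analysis used, so that the final curve can be compared with it.
- **Optional:** a separately labelled curve for revision of any component, and a note in 7.15 that the SAP designates survival as primary.

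The cost is wording only, with no new visits or data and no new analysis unless the optional curve is added. Before signing off, confirm that the CRF, which was not available, records whether the stem was revised, and that the TFL shells use the same event.
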